## **1. BACKGROUND AND RATIONALE**

Varicose veins of the lower limbs affect many people worldwide with incident reports of its extent in 40% of women and 20% of men. Varicose veins occur as a result of weakening valves in veins, causing reversal of blood flow and venous reflux. Risk factors for varicose veins includes family history, obesity, prolonged standing, gender and number of offspring. Symptomatic presentation of varicose veins varies from itching, hyperpigmentation to phlebotic lymphedema, chronic swelling of legs, lipodermatosclerosis, and venous ulcerations. Current treatment options include vein stripping, thermal ablation therapy, such as endovenous laser ablation and non-thermal methods such as Venaseal and Clarivein. The goal of these treatments is to eliminate sources of reflux in order to control the progression of the disease, prevent recurrence and provide symptomatic relieve.

However, given the invasive and surgical nature of these current therapies, some patients do not undergo treatment in fear of the potential surgical complications and prolonged recovery periods. These invasive procedures are also associated with risks of infections and low cost-effectiveness. As such, novel non-invasive therapies are being researched and developed to better meet the need of patients with varicose veins.

More recently, echotherapy technology such as Sonovein®, a high intensity focused ultrasound (HIFU) treatment, has been introduced as a non-invasive alternative for the treatment of varicose veins. During echotherapy treatment, non-invasive high intensity ultrasound beam is focused on the troubled vein, delivering thermal energy. The vein then absorbs the thermal energy, shrinks, and is sealed. The non-invasive nature of echotherapy has the capacity to prevent infections, leaves no scars and discolouration, and removes the need for tumescence anaesthesia. Recovery period from echotherapy is also immediate and caters to all vein types. Further, the administration of echotherapy does not require the presence of external nurses, additional materials such as micro puncture kits, recovery or sterile rooms, making it a more cost-effective treatment compared to current invasive standards of care.

Currently, such high intensity focused ultrasound treatments have only been very recently been introduced as a treatment option for the local population. In this study, we wish to evaluate the safety, efficacy, and performance of HIFU, using the Sonovein® device for our local population. Although it has been shown to be safe and efficacious in its pre-clinical trials, these studies have been limited to generally a caucasian-based population, where the vein size, anatomy and distribution of venous incompetence can be different from their asian counterparts. The pain scores, compliance, quality of life scores, occlusion rate at baseline, 2 weeks, 3 months, 6 months and 12 months will be assessed.

## **2. HYPOTHESIS AND OBJECTIVES**

Primary Objective:

The aim of the study is to evaluate the efficacy of non-invasive echotherapy for the treatment of varicose veins, within local population, using the Sonovein® device. The quality of life scores at baseline, 2 weeks, 3 months, 6 months and 12 months will be assessed using the EQ-50D, AVVQ and CIVIQ scores. Patient satisfaction at these time points will also be assessed.

### **3. EXPECTED RISKS AND BENEFITS**

No additional risk for study patients because they would undergo HIFU as per the assessment by their primary physicians as suitable treatment for the patients. There will not be any study specific interventions for the patients. For this study, we are administering Quality of Life questionnaires, as well as reviewing medical history and procedural information. There will be additional follow-ups arising from participation. There will be a slight inconvenience of multiple returns to clinic and taking time for questionnaires, minimal risk for breach of confidentiality. However, in terms of standard care, this is above and beyond what is expected.

Subjects stand to benefit from the closer monitoring post-procedure. In the long run, the medical knowledge gain with regards to treatment outcomes is beneficial for future patients.

### **4. STUDY POPULATION**

#### **4.1. List the number and nature of subjects to be enrolled.**

15 subjects from inpatient / outpatients from Department of Vascular Surgery, Singapore General Hospital that will be undergoing HIFU for treatment of symptomatic varicose veins will be recruited if they are found to have primary great saphenous (GSV), small saphenous vein (SSV) or anterior accessory saphenous vein (AASV) incompetence on colour duplex scan.

#### **4.2. Criteria for Recruitment and Recruitment Process**

Patients diagnosed with venous reflux on duplex scan and has decided on HIFU as treatment modality will be screened by primary care consultant. The procedure and risk/benefits, as well as other alternative treatment modalities will be explained to patient. At the same time, they will be briefed about the study (what to expect, such as questionnaires and additional follow-ups arising from participation). There will be sufficient time and opportunity given to ask any questions with regards to procedure and study. Patients will be given enough time to consider their participation and can let the study team know of this decision at next visit / surgery day. Should patient be agreeable, informed consent will be taken.

#### **4.3. Inclusion Criteria**

To participate in study, all the following inclusion criteria must be met:-

1. Age >21 years, able to understand the requirements of the study and provide informed consent.
2. C2 – C5 varicose veins / CVI
3. Symptomatic primary GSV, SSV or AASV incompetence, with reflux >0.5 seconds on colour duplex, including one or more of the following symptoms: aching, throbbing, heaviness, fatigue, pruritus, night cramps, restlessness, generalized pain or discomfort, swelling.
4. Patients who has GSV, SSV or AASV diameters of 3mm to 12mm in the standing position.

[figure not shown]
#### 4.4. Exclusion Criteria

Subject will not be eligible for the study if any of the following exclusion criteria is met:-

1. Current DVT or history of DVT
2. Recurrent varicose veins
3. Pregnant patients
4. Arterial disease (ABPI<0.8)
5. Sepsis
6. Patients who are unwilling to participate
7. Inability or unwillingness to complete questionnaires
8. Adverse reaction to sclerosant or cyanoacrylate
9. GSV, SSV or AASV severely tortuous
10. Life expectancy < 1 year
11. Active treatment for malignancy other than non-melanoma skin cancer
12. Current, regular use of systemic anticoagulation (e.g. warfarin, heparin)
13. Daily use of narcotic analgesia or NSAIDS to control pain associated with venous disease

#### 5. STUDY DESIGN AND PROCEDURES/METHODOLOGY

The study involves prospective data collection of 30 patients that will be undergoing HIFU as choice of treatment for their varicose veins / CVI. Questionnaires will be conducted at 5 timepoints – baseline before procedure, 2 weeks, 3 months, 6 months and 12 months. Subjects will be seen at outpatient clinic post-procedure. Besides questionnaires, physical examination and duplex ultrasound scan will be conducted at 2 weeks, 3 months, 6 months and 12 months to ensure occlusion of treated vein.

3, 6 and 12 months: follow-up in clinic with VCSS, AVVQ, CIVIQ and EQ-5D as well as targeted duplex scan to look for anatomical recurrence

Analysis of results and cost evaluation

Physical Examination includes the assessment of:-

- GSV/SSV/AASV reflux
- CEAP Classification (Clinical, Aetiological, Anatomical and Pathophysiology)
- Venous Clinical Severity Score (VCSS)

Duplex ultrasound will be performed by vascular sonographers / vascular consultants. Reflux is determined at the sapheno-femoral (SF) / sapheno-popliteal (SP) junction in the lying and standing position using the Valsalva manoeuvre or manual distal compression with rapid release respectively. Reflux as documented by ultrasound is defined and considered significant as retrograde flow of >0.5 seconds.

Quality of Life questionnaires include:-

- ED5Q
- CIVIQ-14
- AVVQ (Aberdeen Varicose Vein Questionnaire)
- Pain Diary
- Patient Satisfaction Survey

Sonovein® is a unique echotherapy solution, combining therapeutic ultrasound and ultrasound for monitoring. The high-intensity ultrasound beam is focused on the vein through a magnifying glass. As thermal energy is delivered, the thermocoagulation property of ultrasound energy affects the vein wall, causing shrinking and collapsing of the target vein. Thus creating a fibrotic seal and occluding the vessel. The treated vein is immediately closed after the procedure, and its diameter will continuously reduce over time, becoming a fibrotic chord. The treatment along the vein is steered automatically via a touch screen monitor. In-beam linear ultrasound probe allows visualisation of the vein in real-time and insures optimal accuracy.

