## **8. SAMPLE SIZE AND STATISTICAL METHODS**

### **8.1. Determination of Sample Size**

A pilot group of 15 patients will be recruited for this prospective study to investigate the safety and efficacy of HIFU for the treatment of varicose veins.

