### **8.2. Statistical and Analytical Plans**

Categorical data will be presented as frequency (percentage). Numeric data will be presented as mean (standard deviation) for parametric distribution and median (interquartile range) for non-parametric distribution.

The primary endpoint of complete closure at different time points will be reported as frequency and percentage (95% CI). Comparisons of the quality of life and functional results at baseline and after treatment at different time points will be examined using pair t-test or Wilcoxon Signed Rank test, where appropriate.

A two tailed, p-value of <0.05 was considered statistically significant. Statistical analysis will be performed with SPSS statistical software, version 19.0 (IBM Corp. Armonk, NY).

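### The protocol gives two enrolment numbers for the same study, 15 patients in sections 4.1 and 8.1 and 30 in section 5, and does not reconcile them

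*Protocol*

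**What the plan says.** The protocol states the planned enrolment three times.

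- Section 4.1, whose heading asks for the number of subjects: "15 subjects from inpatient / outpatients from Department of Vascular Surgery, Singapore General Hospital that will be undergoing HIFU for treatment of symptomatic varicose veins".
- Section 5, in the sentence that opens the study design: "The study involves prospective data collection of 30 patients that will be undergoing HIFU".
- Section 8.1, on sample size: "A pilot group of 15 patients will be recruited for this prospective study to investigate the safety and efficacy of HIFU".

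Section 8.2 makes complete closure of the vein the primary endpoint, to be given at each time point as a frequency and a percentage with a 95% CI. Quality of life and functional results are compared with baseline by paired tests at the two-sided 5% level. Neither section 8.1 nor section 8.2 gives an expected closure rate, a target interval width, a power or a dropout rate.

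**The concern.** The number of patients is a basic design figure, and here it differs twofold within one document. The closure endpoint has no hypothesis test and no precision target, so the number enrolled alone determines how precisely the trial can estimate the closure rate. With two numbers in the text, a reader cannot tell what precision was planned or when recruitment is complete.

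There is a secondary point. The protocol plans no interim look and no staged enrolment, but section 5 has duplex scans from 2 weeks after the procedure, so early closure results would become known to the study team. While both numbers stand, ending at 15 or going on to 30 could each be said to follow the protocol. Nothing suggests that this is intended, but a choice made after early results could not be shown to be independent of them.

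This is not a matter for a separate statistical analysis plan. Such a plan could repeat one of the numbers, but it could not make both statements in the protocol true.

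**Working it through.** **1. Is there a figure to reproduce?** No. The protocol gives no formula or inputs for either 15 or 30. The check is therefore whether the three statements agree and, if not, whether anything in the text links them.

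**2. The statements side by side.**

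| Place | Number | Unit | Group described |
|---|---|---|---|
| Section 4.1 | 15 | subjects | undergoing HIFU |
| Section 5 | 30 | patients | undergoing HIFU |
| Section 8.1 | 15 | patients | pilot group, HIFU |

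The difference is 30 − 15 = 15 patients, and the ratio is 30 / 15 = 2. Rounding cannot explain it.

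**3. Readings that might reconcile them.**

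- *A pilot of 15 within a study of 30.* Section 8.1 recruits the pilot group for this study itself, section 4.1 gives 15 as the number to be enrolled without calling it a pilot, and no later cohort or expansion is described.
- *A dropout allowance.* None is stated. Inflating by N / (1 − d), 15 / (1 − d) = 30 requires d = 1 − 15/30 = 50%.
- *Limbs or veins instead of people.* Section 5 says patients.
- *A comparison group of 15.* None is described, and all 30 in section 5 undergo HIFU.

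None of these is supported by the text.

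**4. What the difference means for the primary endpoint.** The protocol gives no closure rate and no CI method, so the following rests on assumptions: the closure rates shown, one independent observation per patient, and exact (Clopper-Pearson) 95% limits. For x closures in n patients,

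- lower limit = 2.5% quantile of Beta(x, n − x + 1);
- upper limit = 97.5% quantile of Beta(x + 1, n − x), and 100% when x = n.

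| Assumed closure | n = 15 | Width (points) | n = 30 | Width (points) | Width ratio |
|---|---|---|---|---|---|
| 80% | 12/15: 51.9% to 95.7% | 43.8 | 24/30: 61.4% to 92.3% | 30.9 | 1.42 |
| 86.7% | 13/15: 59.5% to 98.3% | 38.8 | 26/30: 69.3% to 96.2% | 27.0 | 1.44 |
| 93.3% | 14/15: 68.1% to 99.8% | 31.8 | 28/30: 77.9% to 99.2% | 21.3 | 1.50 |

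If every patient's vein closed, the lower limit would be 78.2% with 15/15 and 88.4% with 30/30.

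As a rough check, width falls approximately with the square root of n, which gives √(30/15) = 1.41, close to the ratios in the table.

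**The case against.** The strongest reply is that the text leans clearly towards 15. The two sections whose purpose is to set the number agree, and the 30 appears once, in an introductory sentence, perhaps carried over from another version. The study is an uncontrolled pilot with a descriptive primary endpoint, so no power claim or pass/fail decision fails at either number. The stopping remark describes a possibility, not a plan: no look at the data or continuation rule is written down, and section 11 makes the investigator responsible for informing the CIRB of protocol amendments. The interval widths rest on assumed closure rates, and section 8.2 does not say whether closure is counted per vein or per patient. The front pages and a figure in the protocol were not available to read.

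Much of this is fair. The weight of the text does favour 15, no calculated figure in the protocol is wrong, and the widths are illustrations. The stopping argument is a secondary reason to settle the number and should not carry the finding. The unseen material limits how firmly one can say that nothing anywhere explains the 30. None of this removes the contradiction. The document does not say that the 30 is a leftover, and an unseen explanation would still leave sections 4.1, 5 and 8.1 disagreeing as they stand.

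**Conclusion.** The concern holds. The planned enrolment is stated as 15 in two places and 30 in a third, for the same single group of patients, and no text that could be read reconciles them. The documented size of the error is 15 patients, a factor of two. Its consequence for the closure interval is a width about 1.4 to 1.5 times greater at 15 than at 30, for assumed closure between 80% and 93%, exact limits and one independent observation per patient. The contradiction itself needs none of those assumptions. Which number was approved cannot be determined from the document. Because this figure sets the precision of the primary endpoint, it must be corrected and is more than an editorial slip.

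**What to change.** Confirm the approved enrolment number and state it identically in sections 4.1, 5 and 8.1, before closure results are looked at. The protocol does not show the trial's status; if results have already been seen, record when and on what basis the number was settled.

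- **If 15 is confirmed:** change the 30 in section 5 to 15. No extra patients are needed. The cost is accepting lower precision than the 30 would imply.
- **If 30 is confirmed:** change the 15 to 30 in sections 4.1 and 8.1. This means recruiting 15 more patients than those sections state and following them to 12 months.

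Either way the document change is one wording amendment, of which the CIRB should be informed as section 11 requires.

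### Does the protocol leave out a pre-procedure VCSS that its comparisons with baseline would need?

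*Protocol*

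**What the plan says.** Section 5 gives the questionnaires five time points: "baseline before procedure, 2 weeks, 3 months, 6 months and 12 months". It then states that "Subjects will be seen at outpatient clinic post-procedure", and continues that "physical examination and duplex ultrasound scan will be conducted at 2 weeks, 3 months, 6 months and 12 months", with the aim of confirming that the treated vein has closed. A separate line covers months 3, 6 and 12: "follow-up in clinic with VCSS, AVVQ, CIVIQ and EQ-5D as well as targeted duplex scan to look for anatomical recurrence". Further down, an undated list gives the content of the physical examination: reflux, CEAP classification and VCSS.

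Baseline is mentioned in three other places:

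- Section 1 lists "pain scores, compliance, quality of life scores, occlusion rate at baseline, 2 weeks, 3 months, 6 months and 12 months".
- Section 2 has quality of life "at baseline, 2 weeks, 3 months, 6 months and 12 months will be assessed using the EQ-50D, AVVQ and CIVIQ scores".
- Section 8.2 plans a paired t-test or Wilcoxon signed-rank test of quality of life and functional results, before against after treatment. It does not define functional results. Its primary endpoint is complete closure.

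**The concern.** Section 5 sets two schedules next to each other. One names a time point before the procedure and the other does not, and VCSS falls under the second. A reader may infer that the severity score is first taken at 2 weeks.

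The protocol describes no control group, so any improvement in VCSS can be shown only against the patient's own score before treatment. Both tests in section 8.2 need a baseline value from each patient. If functional results means VCSS and no score is taken beforehand, that comparison is impossible, because a clinician-rated score cannot be reliably reconstructed later. The loss would be confined to VCSS. Closure, quality of life, reflux and clinical class would be unaffected.

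**Working it through.** The protocol gives no figure to reproduce, so the check is a comparison of the relevant places.

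**1. Count of mentions.** Baseline appears four times, once each in sections 1, 2, 5 and 8.2. VCSS appears twice, both times in section 5: once in the undated examination list and once in the line for months 3, 6 and 12. No statement joins the two. The observation behind the concern is therefore accurate; the question is what follows from it.

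**2. What the examination sentence covers.** It comes directly after the statement that patients are seen in clinic after the procedure, and its purpose is to check closure. That purpose has no meaning before treatment. The sentence lists follow-up visits and does not say that examinations happen only then.

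**3. Test of reading it as exhaustive.** If the four time points were complete, there would be no duplex scan and no clinical classification before treatment. The protocol shows otherwise:

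| Item in the examination list | Evidence that it is assessed before treatment |
|---|---|
| Reflux | Sections 4.1 and 4.2 require incompetence or reflux on duplex; section 4.3 sets the threshold at more than 0.5 seconds |
| CEAP classification | Section 4.3 admits clinical classes C2 to C5 |
| VCSS | No explicit statement either way |

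Two of the three items are assessed before the procedure although the sentence gives no such time point. Its silence is therefore no evidence that the third is omitted. Section 4.2 also provides a contact at which an examination can take place, since a patient who "has decided on HIFU as treatment modality will be screened by primary care consultant".

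**4. Test of the line for months 3, 6 and 12.** This line names VCSS together with AVVQ, CIVIQ and EQ-5D. Sections 2 and 5 put the quality-of-life questionnaires at baseline and 2 weeks as well, and the line shows neither. If it were a full schedule, it would also remove the baseline for quality of life, which the protocol states expressly. So the missing baseline in this line says nothing about VCSS.

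The line and the next one, on analysis of results and cost evaluation, interrupt the prose and read like the last two boxes of a flow chart. Such a chart would normally have earlier boxes for enrolment, procedure and the 2-week visit. Figures are not reproduced in the text reviewed, and a baseline box could well list the same instruments.

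**5. Test of the link to section 8.2.** There are two cases:

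- Functional results means something other than VCSS. Then no planned analysis needs a baseline VCSS.
- Functional results means VCSS. Then section 8.2 itself presupposes a VCSS before treatment, and section 5 does not deny it.

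Neither case produces a contradiction.

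**The case for a change.** The strongest opposing argument is that timing of an examination belongs in the protocol. A statistical analysis plan can define functional results, but it cannot supply a score that nobody recorded. For reflux and clinical class, the eligibility criteria fill the silence of section 5; for VCSS no visible text does. Section 8.2 names quality of life separately, so functional results must be something else, and VCSS is a plausible candidate. A team working from the prose alone is not told to score VCSS before the procedure.

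Part of this stands. The prose would be clearer if it named a baseline VCSS, and an explicit statement would cost almost nothing.

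It does not make an error, however. The argument needs three things together: that the missing part of the apparent flow chart has no baseline VCSS, that functional results means VCSS, and that the examination sentence is exhaustive. The first cannot be established from the available text, the second is only an inference, and the third fails against the protocol's own eligibility criteria. Defining an analysis variable is also commonly left to the analysis plan, which is not at hand.

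**Conclusion.** The concern does not hold. The protocol does not explicitly place VCSS at baseline in the text available, but it does not exclude it and contradicts nothing by its silence. VCSS is not named as an endpoint: section 8.2 makes complete closure primary, and section 2 names quality of life and satisfaction. No sample size, test, threshold or stated result depends on this point.

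The conclusion rests mainly on reading the examination sentence as a list of follow-up visits, which its context and the eligibility criteria support. It is strengthened by the assumption that the two detached lines in section 5 come from a flow chart with earlier boxes. That assumption is likely but cannot be confirmed here.

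The view would change if the complete protocol showed a schedule with no VCSS before the procedure and the analysis plan also named VCSS change as a result to be tested.

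### Safety is a stated purpose, but apart from pain no scheduled visit specifies a solicited complication check, so complication counts will be unsystematic and probably too low

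*Protocol*

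**What the plan says.** **Safety as a purpose.** Section 1 of the protocol says "we wish to evaluate the safety, efficacy, and performance of HIFU, using the Sonovein® device for our local population". Section 8.1 recruits the pilot group "to investigate the safety and efficacy of HIFU for the treatment of varicose veins". Section 1 also says that the treatment "has the capacity to prevent infections, leaves no scars and discolouration". The formal objective in section 2 is narrower: "The aim of the study is to evaluate the efficacy of non-invasive echotherapy for the treatment of varicose veins".

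**What the visits contain.** Section 5 states that "physical examination and duplex ultrasound scan will be conducted at 2 weeks, 3 months, 6 months and 12 months to ensure occlusion of treated vein". For 3, 6 and 12 months it also lists a "targeted duplex scan to look for anatomical recurrence". The items under "Physical Examination includes the assessment of" are reflux, CEAP class and VCSS. The questionnaires include a pain diary, and section 1 lists pain scores among the repeated assessments.

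**How adverse events are handled.** Section 6.1 defines adverse and serious adverse events as occurrences resulting from the research, and it counts signs as well as symptoms. Under section 6.2, related serious events go to the ethics board and other related events are kept in the site file. Section 6.3, headed as the safety monitoring plan, deals only with anonymising and storing data. Section 3 says that patients would receive HIFU anyway on their physician's assessment and that the research adds no intervention of its own.

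**The concern.** A safety aim needs a defined way of finding harms. Section 5 gives the examination and the scan an efficacy or disease-status purpose. Apart from pain, it names no complication to ask about or look for: no burn, scar, discolouration, infection, altered sensation or thrombus. Whether such an event is recorded then depends on a patient raising it or an examiner happening to note it, and on someone judging it related to the research.

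That last judgement is itself unclear. If HIFU is routine care and the research adds nothing to it, a HIFU burn could be read as falling outside section 6.1 altogether.

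The error would probably run in one direction, towards too few complications. A report of few or none could mean that the treatment is safe in these patients or that nobody looked systematically. An analysis plan cannot repair this, because it cannot recover observations that were never made.

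**Working it through.** **1. Reading the sections together.** The plan gives no complication rate and no safety calculation, so there is no figure to reproduce. The question is whether any section supplies a solicited complication check.

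| Place in protocol | What it supplies | Solicited complication check? |
|---|---|---|
| Section 5, examination and scan at 2 weeks, 3, 6 and 12 months | Occlusion of the treated vein | None named |
| Section 5, scan at 3, 6 and 12 months | Anatomical recurrence | None named |
| Section 5, examination items | Reflux, CEAP, VCSS | None named; the list is open |
| Sections 1 and 5, pain scores and pain diary | Pain | Yes, for pain only |
| Sections 6.1 and 6.2 | Recording of research-related events | No visit, question or method given |
| Section 6.3 | Data storage and anonymisation | No |

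Pain is the only harm that is solicited. The active seeking of follow-up information in section 6.2 concerns cases already known to qualify for reporting, so it does not find new ones.

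**2. Scale, for illustration only.** Inputs:
- n = 15 (sections 4.1 and 8.1) or n = 30 (section 5). The protocol gives both, so both are shown.
- r, the true complication rate, and c, the share of cases captured. Both are assumptions; the documents give neither.

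Formula: P(no case recorded) = (1 − r × c)^n.

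| r | c | n = 15 | n = 30 |
|---|---|---|---|
| 10% | 100% | 0.90^15 = 0.206 | 0.90^30 = 0.042 |
| 10% | 50% | 0.95^15 = 0.463 | 0.95^30 = 0.215 |
| 10% | 25% | 0.975^15 = 0.684 | 0.975^30 = 0.468 |
| 5% | 100% | 0.95^15 = 0.463 | 0.95^30 = 0.215 |
| 5% | 50% | 0.975^15 = 0.684 | 0.975^30 = 0.468 |

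Halving capture has the same effect as halving the true rate. With full capture nothing is lost.

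**3. What zero recorded cases would allow one to say.** The exact two-sided 95% upper limit is 1 − 0.025^(1/n), which is 21.8% at n = 15 and 11.6% at n = 30. These limits hold for the true rate only if every case is captured. At 50% capture they bound r × c, so the limits for r become 0.218 / 0.5 = 43.6% and 0.1157 / 0.5 = 23.1%.

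**The case against.** A reader might infer that no complication is looked for at any visit and that the safety question cannot be answered. The protocol does not support that:
- Pain is solicited.
- The examination list is introduced by a word that leaves it open ("Physical Examination includes the assessment of").
- Adverse events include signs, and the leg is examined and scanned at four visits by people who could notice one. Nothing shows that a thrombus visible on the scan would be missed.
- CEAP and VCSS touch on skin status.
- Related events are recorded and related serious events reported, so some safety data would exist.

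A reader might also count the lack of a safety endpoint in section 8.2 as a defect. It is not one here, because that can be left to an analysis plan that is not shown.

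Three further points deserve weight. Safety is missing from the formal objective in section 2, so its standing is lower than that of efficacy. The line on the 3-, 6- and 12-month visits in section 5 looks like the remains of a flow chart, so some content for other visits may have been lost in extraction. The data collection sheet mentioned in section 7.2 is not shown and might hold a checklist. The 50% capture is also no more than an assumption, and with four examinations the true figure may be higher.

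These points remove the absolutes but leave the core. Safety is named as a purpose in two sections. The sentence in section 5 that covers all four visits is intact prose and gives an occlusion purpose. Being able to notice a complication is not the same as having to record its presence or absence in every patient.

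**Conclusion.** The point holds in this form: safety is a stated purpose, yet apart from pain no scheduled visit in section 5 specifies a solicited complication assessment. Safety therefore rests on unsolicited recording, limited to events related to the research. Sections 3, 6.1 and 6.2 leave open whether complications of HIFU itself qualify. Complication rates would be ascertained unsystematically and are probably too low, so a finding of few or none could not be relied on.

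The size cannot be derived from the protocol. Under an assumed 10% rate and 50% capture, the chance of recording no case rises by about 26 percentage points at n = 15 (46.3 − 20.6) and about 17 at n = 30 (21.5 − 4.2). The loss shrinks to nothing as capture approaches 100% and grows below 50%. The efficacy endpoints are not affected.

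**What to change.** 1. In section 5, add to the existing examinations at 2 weeks, 3, 6 and 12 months a yes/no record, over the treated segment, of burn, scar, discolouration, infection and altered sensation.
2. Record the same skin and sensation items before the procedure. C2 to C5 patients are enrolled, and skin change already present should not be counted as a complication.
3. On the duplex scans already scheduled, record thrombus at the treated junction as present or absent.
4. Reconcile sections 3, 6.1 and 6.2 so that it is clear whether complications of HIFU count as recordable adverse events.

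The cost is one extra form page, a few minutes per visit (an estimate) and a short added baseline check, since section 5 schedules only questionnaires at that point. No new visit is needed. The reported complication rate may turn out less favourable, but an absence of complications would then be an observed result.
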